MRC	Medical Research Council	
NDAU	Neonatal Data Analysis Unit	
NHS	National Health Service	
NICE	National Institute for Clinical Excellence	
NNRD	National Neonatal Research Database	
OASIS	Obstetric Anal Sphincter Injuries	
PI	Principal Investigator	
PIS	Participant Information Sheet	
QA	Quality Assurance	
R&D	Research and Development	
REC	Research Ethics Committee	
SAP	Statistical Analysis Plan	
SOP	Standard Operating Procedure	
SMF	Study Master File	
SMG	Study Management Group	
SSC	Study Steering Committee	
UKNC	UK Neonatal Collaborative	

**1 Amendment History** The following amendments and/or administrative changes have been made to this protocol since the implementation of the first approved version.

Amendment No. (specify substantial/non- substantial)	Protocol version no.	Date issued	Summary of changes made since previous version

# 2 Synopsis

Short title	The POOL Study
Internal ref. no.	
Funder and ref.	NIHR HTA 16/149/01
Study design	A cohort study with nested qualitative component
Study participants	The main analysis will include women who use water immersion during labour
	at NHS study sites. Descriptive data will be reported on all women at study
	sites.
Planned sample size	30,000 women
	16,200 babies
Inclusion criteria	Women who give birth in a participating site who do not opt-out.
Exclusion criteria	Women who have opted-out.
Treatment duration	N/A
Follow-up duration	To midwifery discharge
Planned study period	April 2018 – August 2021
Primary objective	To establish whether for 'low-risk' women who use a pool during labour,
	waterbirth, compared to leaving a pool prior to birth, is as safe for mothers
	and babies.
Secondary objectives	Secondary study objectives are to:
	1) Describe the indications and maternal and neonatal outcomes for women
	who use a pool during labour and who have risk factors at labour onset, or
	develop complications during labour;
	2) Amongst women who left the pool prior to birth, describe the reasons birth
	occurred out of water.
	3) Explore factors associated with high and low rates of pool use in individual
	maternity units;
	4) Describe the demographic and obstetric characteristics, of women using a
	birth pool for labour and birth.
Primary outcomes	Maternal primary outcome: Obstetric Anal Sphincter Injuries (OASIS).
	Neonatal primary outcome: A composite of 'adverse neonatal outcomes or

TPL/003/2 v1.0

Page **8** of **38** 

Secondary outcomes	atment' to include: (a) any neonatal unit admission requiring respiratory oport (b) antibiotic administration within 48 hours of birth (with or without ture proven infection); and (c) intrapartum stillbirth or neonatal death. ternal secondary outcomes: Maternal Intrapartum: Shoulder dystocia d required management, management of the third stage of labour, ether the placenta, was intended to be, or was, delivered in or out of
Secondary outcomes	ture proven infection); and (c) intrapartum stillbirth or neonatal death. ternal secondary outcomes: Maternal Intrapartum: Shoulder dystocia d required management, management of the third stage of labour,
Secondary outcomes Ma	ternal secondary outcomes: Maternal Intrapartum: Shoulder dystocia d required management, management of the third stage of labour,
· · · · · · · · · · · · · · · · · · ·	d required management, management of the third stage of labour,
· · · · · · · · · · · · · · · · · · ·	d required management, management of the third stage of labour,
and	
	ether the placenta, was intended to be, or was, delivered in or out of
wh	
wat	ter), need and reason for obstetric involvement in woman's care
incl	luding sepsis, maternal position at birth, treatment for haemorrhage,
inci	idence and management of perineal and other genital trauma. Maternal
Pos	stnatal: duration of postnatal stay, breast feeding, higher level care, and
ma	ternal readmission to hospital within seven days of birth.
Infa	ant secondary outcomes: Snapped umbilical cord prior to clamping,
res	uscitation, Apgar scores. Incidence of: culture proven infection; brachial
ple	xus injury; treatment for jaundice; readmission to hospital within seven
day	rs of birth; therapeutic hypothermia; neonatal unit admissions; cause of
nec	onatal death; respiratory support.
Intervention Birt	th in water following water immersion during labour

### 3 Study summary

The POOL Study is a cohort study with a nested qualitative component. The primary study aim is to establish whether for 'low-risk' women who use a pool during labour, waterbirth, compared to leaving a pool prior to birth, is as safe for mothers and babies. The criteria for women being 'low-risk' will follow criteria set out in the NICE Intrapartum Care Guidelines (1). Pool use during labour includes all forms of water immersion including permanent and temporary birth pools and conventional baths.

Primary study objectives are to:

- Evaluate if waterbirth is associated with an increase in adverse neonatal outcomes or treatment, to include asphyxia, infection, respiratory difficulties, and mortality; or maternal morbidity, particularly complex perineal trauma (Obstetric Anal Sphincter Injuries (OASIS)) and haemorrhage.
- 2. Assess the primary safety outcomes amongst the subgroups of nulliparous and parous women who were low risk at labour onset.
- Describe rates and treatment of haemorrhage for low risk women who, following birth in water, deliver the placenta underwater. This will also be described for women who leave the water prior to delivery of the placenta.

The secondary study objectives will set pool use and waterbirth in the context of NHS care. The study will describe:

- 1. The overall proportion and characteristics of women who use a pool for labour or birth, compared to those who do not use a pool.
- 2. The characteristics of, and outcomes for, women with identified risk factors at labour onset, who use a pool during labour.
- 3. The characteristics of, and outcomes for, women who develop labour complications who use a pool during labour.
- 4. Explore factors associated with high and low rates of pool use in individual maternity units.

### 3.1 Study lay summary

It is estimated that up to 60,000 (9 in every 100) babies are born into water annually in the UK and with encouragement from NICE for maternity units to provide birthing pools for women, this

Page **10** of **38** 

number may increase further. Women use a birth pool during labour for pain relief, and some women choose to remain in the pool for the birth of their baby.

Over the years there have been reports of babies that had breathing difficulties or infection following birth in water, and there is a concern that women that have a waterbirth more often sustain severe trauma to their vaginal area or have unrecognised heavy bleeding. Despite concern, and some reports in the press, to date there have not been studies large enough to show whether or not waterbirth causes an increase in these poor outcomes for mothers or their babies.

This study plans to answer the question about the safety of waterbirths. The study will collect data on the births of all women in around 30 maternity units during 2015-2020. The study will determine how many women are using birth pools, how many women give birth in water and whether mothers or their babies come to any extra harm as a result of waterbirth. The study will include women giving birth to their first baby and women giving birth to a subsequent child.

The study needs to collect information on 15,000 waterbirths and 15,000 births out of water. To do this without disturbing women in labour or just after birth, when they are looking after their new baby, the study will use information collected as part of each woman's and linked baby maternity record stored at hospitals in computerised systems. For babies that need specialist care after birth, the study will also use data held by the National Neonatal Research Database (NNRD). Some of the data needed for this study is already collected by maternity units, so data from births from 2015 onwards can be included in the study. However, as some important information needed to fully answer the study questions, such as how many babies have antibiotics, and how many women deliver the placenta underwater, is currently not collected, some new items will be added to maternity computer systems when the study starts in 2018. To keep women's information confidential, the data stored in existing maternity information systems will have identifying information, such as names, addresses and NHS numbers removed before the information is sent to the research team in Cardiff for analysis.

Professionals and parents have strong opinions on waterbirth. Some are great advocates, who promote the potential benefits of waterbirth to women, whilst others remain concerned that women may be taking additional unnecessary risks by giving birth in water. The diversity of opinions towards waterbirth makes it particularly important that the study team have representatives from all interested groups. The professionals on the study team include midwives, an obstetrician and a neonatologist as well as the experts needed to deliver this large complex study. The NCT is the

TPL/003/2 v1.0

Page **11** of **38** 

largest parenting organisation in the UK and have joined the study team as have the Royal College of Midwives.

The study will produce academic papers and evidence based information for women and their partners on waterbirth. The study findings will be of great interest and would be expected to generate much press interest, and quickly influence the information provided to pregnant women throughout the UK.

### 4 Background

During labour and birth water immersion is facilitated by use of a conventional bath or more frequently a specialist birthpool. All birthpools offer sufficient depth of warm water for the woman to be immersed to above her breasts when sitting and sufficient space for ease of movement and change of position. Simple inflatable pools are available, but NHS maternity units frequently now have pools which are plumbed in, some of which are more complex with inbuilt lighting and heating. Women enter the warm water in established labour, leaving the pool either prior to birth due to clinical concerns or maternal choice, or remaining in the pool until after birth of the baby. Some mothers remain in the pool until after delivery of the placenta. For mothers the potential benefits of waterbirth are considered to be pain reduction, relaxation, reduced labour interventions and reduced perineal trauma whilst for babies, a gentle birth and transition to life. It is suggested that waterbirth may also improve longer term outcomes; mother infant bonding, increased breastfeeding and enhanced maternal postnatal mental health.

In 1992 the House of Commons Health Committee recommended that hospitals should provide women with the use of a birth pool for labour '*where this is practicable*. In the intervening years the popularity of the use of water immersion for labour and birth in the UK has increased and NICE guidance has recommended since 20071.4 that water immersion analgesia should be made available to all clinically appropriate women in labour. The Cochrane review of water immersion during labour provided evidence supportive of pool use but could not answer the question relating to the safety of waterbirth. The review included 12 trials (3243 women), eight related to just the first stage of labour: one to early versus late immersion in the first stage of labour; two to the first and second stages; and another to the second stage only. Results for the first stage of labour found a significant reduction in the epidural/spinal/paracervical analgesia/anaesthesia rate amongst women allocated to water immersion compared to no immersion (478/1254 versus 529/1245; risk ratio (RR) 0.90; 95% confidence interval (Cl) 0.82 to 0.99, six trials). There was also a reduction in duration of the first stage of labour (mean difference -32.4 minutes; 95% Cl -58.7 to -6.13). There was no evidence

TPL/003/2 v1.0

Page **12** of **38** 

of a difference in the rates of assisted vaginal deliveries (RR 0.86; 95% CI 0.71 to 1.05, seven trials), caesarean sections (RR 1.21; 95% CI 0.87 to 1.68, eight trials), use of oxytocin for augmentation (RR 0.64; 95%CI 0.32 to 1.28, five trials), perineal trauma or maternal infection. Of the three trials that compared water immersion during the second stage with no immersion, one trial found a significantly lower level of maternal satisfaction with the birth experience out of water (RR 0.24; 95% CI 0.07 to 0.80). The outcomes for babies following waterbirth has more recently been reported in a systematic review of 29 studies. Whilst the review found no evidence of a difference in clinically important neonatal outcomes for babies born in water, it concluded that a large multicentred study to address the question of the safety of waterbirth for babies is now a priority.

The analgesic properties of water immersion during labour make the option attractive to women and the relatively low cost of the purchase and installation of birthpools, at around £5,000 per pool, makes this a reasonable facility to be provided within NHS premises. Whilst the provision of birthpools are desirable in order to provide women with comfort in labour, if waterbirth is associated with an increase in adverse maternal or neonatal outcomes the potential economic and social costs, could be very high. Several case reports have highlighted potential safety issues for babies that are manifest in the days after birth. Some potential adverse outcomes of clinical interest are specific to waterbirth such as neonatal water inhalation, whilst for other outcomes, being in a pool has the potential to adversely influence outcomes, such as in the time-critical emergency management of shoulder dystocia, which could potentially be delayed due to the need to move the woman from the pool. Such adverse outcomes, in addition being devastating to families are costly to the NHS with a daily tariff for neonatal intensive care at £1,081 and settlements for cerebral palsy resulting from clinical negligence with potential values of over £10m^8. Whilst water immersion is accepted to provide effective labour analgesia, evidence continues to be lacking as to whether women should be encouraged to leave, or remain in, the pool for birth.

### 5 Study objectives/endpoints and outcome measures

The primary study aim is to establish whether for 'low-risk' women who use a pool during labour, waterbirth, compared to leaving a pool prior to birth, is as safe for mothers and babies.

### 5.1 Primary study objectives

1. Evaluate if waterbirth is associated with an increase in adverse neonatal outcomes or treatment, to include asphyxia, infection, respiratory difficulties, and mortality; or

maternal morbidity, particularly complex perineal trauma (Obstetric Anal Sphincter Injuries (OASIS)) and haemorrhage.

- 2. Assess the primary safety outcomes amongst the subgroups of nulliparous and parous women who were low risk at labour onset.
- Describe rates and treatment of haemorrhage for low risk women who, following birth in water, deliver the placenta underwater. This will also be described for women who leave the water prior to delivery of the placenta.

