### 5.4 Secondary Outcomes

Secondary outcomes of parental, clinical and financial importance have been identified. Data relating to maternal or neonatal readmission to hospital within seven days of birth is already reported by community midwives and captured in EuroKing® systems at the point of discharge from midwifery care. Data relating to some primary and secondary outcomes are not currently captured in EuroKing® maternity information systems and at site opening the EuroKing® E3 systems at sites will be amended to prospectively collect these data.

Maternal secondary outcomes: Maternal Intrapartum: Shoulder dystocia and required management, management of the third stage of labour, need and reason for obstetric involvement in woman's care including sepsis; mode of birth, maternal position at birth, treatment for haemorrhage, incidence and management of perineal and other genital trauma. Maternal Postnatal: duration of postnatal stay, breast feeding initiation and continuation, higher level care, and maternal readmission to hospital within seven days of birth.

Infant secondary outcomes: Snapped umbilical cord prior to clamping, skin to skin contact at birth, timing of cord clamping, resuscitation, Apgar scores, administration and duration of intravenous antibiotics. Incidence of: lumbar puncture, culture proven infection, brachial plexus injury; treatment for jaundice; readmission to hospital within seven days of birth; therapeutic hypothermia;

TPL/003/2 v1.0

Page **15** of **38** 

neonatal unit admission and duration; cause of neonatal death; respiratory support. Where available, and where the risk status and pool usage of mothers can be determined, retrospective data will be used in addition to prospective data, to describe the occurrence of these infant outcomes.

Additional data items with accompanying background development required to fully answer the research aims will be added to E3 systems at study sites, and will include:

- Maternal risk factors at pool entry
- Maternal risk factors developing during labour
- Time of entry into pool
- Time of last leaving pool
- Reason for leaving pool if prior to birth
- Partial birth in water (breech / shoulder dystocia)
- Birth position in pool
- Conversion from planned physiological to active third stage labour management.
- Delivery of placenta in or out of water
- Treatment for haemorrhage
- Reason for obstetric involvement in woman's care

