For the neonatal primary outcome, an estimate of 5% is used for the proportion of babies born to 'low risk' mothers experiencing 'adverse neonatal outcome or treatment'. A non-inferiority margin of 1.0% or less will be taken as clinically non-significant. A sample size of 16,200 babies (8,100 per group water / land) are required to have 90% power, and a 95% one sided confidence interval around a treatment difference of zero. The identification of women who leave and do not leave the pool prior to delivery of the placenta can only be captured by addition of new data items in the prospective cohort. As delivery of placenta in water, or postpartum haemorrhage of >1,000 ml following waterbirth are relatively uncommon events (17% and 1% respectively) the proposed sample size of 30,000 women who use a birth pool will be underpowered to detect a difference in these outcomes, but will be described.

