#### Table 1. Potential confounders for both maternal and baby outcomes

#### 9.6.6 Subgroup analysis

Maternal: A planned and powered sub group of the primary maternal outcome will be conducted to compare rates separately for primiparous and multiparous women. One previous cohort study of women using a pool during labour found that delivery of placenta in water and postpartum haemorrhage of >1,000 ml to be relatively uncommon (17% and 1% respectively). It is likely therefore that the proposed sample of 15,000 women who will give birth in a pool during the period of prospective data collection (2018 – 2020) will be underpowered to detect a difference in rates of postpartum haemorrhage between women who remain in, or leave the pool, for delivery of the placenta, but these data and outcomes will be described. The relationship between the proportion of women using a pool during labour, at individual sites and the incidence of adverse maternal and primary outcomes will be described.

TPL/003/2 v1.0

Page 25 of 38

Neonatal: A planned sub group of the primary neonatal composite outcome will also be conducted to compare rates separately for babies born to primiparous and multiparous women.

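### Describing haemorrhage by where the placenta was actually delivered lets early bleeding decide the group, so underwater placental delivery can look safer than it is; intended place and the reason for leaving after birth should be recorded.

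*Protocol*

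**What the plan says.** Section 5.1 of the protocol makes it a primary objective to "Describe rates and treatment of haemorrhage for low risk women who, following birth in water, deliver the placenta underwater", and adds: "This will also be described for women who leave the water prior to delivery of the placenta". Section 9.6.6 returns to the same contrast and calls the sample "underpowered to detect a difference in rates of postpartum haemorrhage between women who remain in, or leave the pool, for delivery of the placenta"; it says the outcomes will be described. Section 9.6.1 gives the background figures, calling underwater placental delivery and haemorrhage above 1,000 ml "relatively uncommon events (17% and 1% respectively".

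The documents differ on what is recorded. The synopsis lists, among maternal secondary outcomes, whether the placenta "was intended to be, or was, delivered in or out of" water. Section 5.4 does not mention intention. Its list of new E3 items has "Delivery of placenta in or out of water" and, for exits, "Reason for leaving pool if prior to birth". The same list also includes the time of last leaving the pool and conversion from a planned physiological to an active third stage.

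For the comparison of birth in water with birth out of water, section 7 restricts Group 2 to low-risk women who left the water for reasons other than clinical need. No similar rule is given for the placental groups.

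**The concern.** The groups in objective 3 form after the birth, during the interval in which haemorrhage can begin. A woman who gives birth in water and means to stay, but bleeds and is helped out before the placenta is delivered, is classified as having left. Her haemorrhage is removed from the underwater group and added to the other one. The outcome then partly determines the exposure, and the error favours underwater delivery whenever women who bleed are more likely to leave than women who do not.

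This is systematic error. The protocol's caveat about the comparison concerns power only, and more data would not remove the bias. The relevant items exist only in the prospective part of the study and are added at site opening, so an intention that was never recorded cannot be restored at the analysis stage. The lay summary names unrecognised heavy bleeding as a concern about waterbirth, so a lower rate in the underwater group could be read as reassurance.

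**Working it through.** **Inputs.** From section 9.6.6: 15,000 women giving birth in a pool in the prospective period. From sections 9.6.1 and 9.6.6: 17% placenta in water and 1% haemorrhage above 1,000 ml. Assumed, because the documents give no value: the fraction f of women intending underwater delivery who bleed and leave before the placenta is delivered. The 17% is used as the intending share. The ratios below do not depend on the 15,000.

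**The plan's own statement.** The protocol gives no power figure for this contrast, only that it is underpowered. The split is 0.17 × 15,000 = 2,550 and 12,450 women. At an overall risk of 1% and a true ratio of 1.5, the risks are 0.01/(0.17 × 1.5 + 0.83) = 0.92% and 1.5 times that, 1.38%. A two-sided 5% test has about 56% power, which agrees with the statement.

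**Reclassification, no other exits.** Let p1 be the risk among the 2,550 intending women. Total events are 150.

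- Observed underwater rate = 2,550·p1·(1 − f) / [2,550·(1 − p1·f)]
- Observed rate among those who left = [150 − 2,550·p1·(1 − f)] / [15,000 − 2,550·(1 − p1·f)]

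With no true effect, p1 = 1% and 25.5 events are expected among the intending women:

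| f | Underwater | Left the water | Observed ratio |
|---|---|---|---|
| 0 | 25.5/2,550 = 1.00% | 124.5/12,450 = 1.00% | 1.00 |
| 0.10 | 22.95/2,547 = 0.90% | 127.05/12,453 = 1.02% | 0.88 |
| 0.30 | 17.85/2,542 = 0.70% | 132.15/12,458 = 1.06% | 0.66 |
| 0.60 | 10.2/2,535 = 0.40% | 139.8/12,465 = 1.12% | 0.36 |

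At f = 0.30 fewer than eight women (25.5 − 17.85 = 7.65) change group.

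**When a true excess is hidden.** The observed ratio reaches 1 when the underwater rate falls to the overall 1%, that is p1(1 − f)/(1 − p1·f) = 0.01, so f = (p1 − 0.01)/(0.99·p1).

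- True ratio 1.5: p1 = 1.3825%, f = 0.003825/0.013687 = 0.28.
- True ratio 2.0: p1 = 1.7094%, f = 0.007094/0.016923 = 0.42.

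Below these values the excess is diluted but still visible. At f = 0.25 a true 1.5 appears as 1.05 and a true 2.0 as 1.37.

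**If women who do not bleed also leave.** Suppose 20% of them leave before the placenta, with the intending share raised to about 21% so that about 17% still deliver underwater. With no true effect the observed ratio is 0.93 at f = 0.25 and 0.58 at f = 0.50, against 0.72 and 0.46 without such exits. With a true ratio of 1.5 it is 1.35 and 0.83, against 1.05 and 0.66. With no true effect, equal leaving fractions in the two kinds of women give no distortion.

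**The case against.** The objective asks only for a description. No test, margin or safety conclusion is attached to it, and a table by actual place is a legitimate account of what happened. Haemorrhage by place of placental delivery is not one of the two primary outcomes and has no part in the sample size. All of this stands, and it limits the severity. It does not make the table neutral: the low-power caveat covers random error only.

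The leaving fraction is assumed. The documents mention leaving for clinical concerns only before birth, so an exit prompted by bleeding in the third stage is a clinical inference. Bleeding that starts after placental delivery cannot move anyone, and no timing split is given. At f = 0.30 the 18 or so underwater events have an exact 95% Poisson interval of about 10.7 to 28.4, which includes the 25.5 expected without reclassification, so bias of that size could not be told from chance. These points also stand.

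A reader might infer that the women concerned cannot be identified at all. The documents do not support that. Time of last leaving the pool, conversion to active third stage, treatment for haemorrhage and reason for obstetric involvement are all listed and give partial identification. None of them records where the woman intended to deliver the placenta or why she left.

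Nor does the omission from section 5.4 prove that intention will go unrecorded. The list is introduced as what the new items will include. It appears incomplete elsewhere: section 7 requires a new field for antibiotics within 48 hours, while the list names only their duration. The synopsis and section 5.4 nevertheless disagree and must be reconciled.

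**Conclusion.** The point holds as a risk of bias in a known direction and of unknown size. Grouping by actual place can make underwater placental delivery look safer than it is, and the data items listed in section 5.4 would correct this only in part. With no true effect and no other exits, f from 0.10 to 0.60 gives observed ratios from 0.88 to 0.36; the bias is smaller if women who do not bleed also leave.

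A reader might go further and infer that underwater delivery will look safe even if it is harmful. The documents do not support that. A true excess is always diluted when women who bleed leave more often than others, but it disappears only above f of about 0.28 (true ratio 1.5) or 0.42 (true ratio 2.0), and nothing in the protocol says whether such fractions occur.

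The primary outcomes and the sample size are untouched. The change is worth making before the E3 fields are fixed, but it is not essential to the validity of the main analysis.

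**What to change.** Carry intended place of placental delivery, as held at the time of birth, from the synopsis into section 5.4 and the list of E3 items. Extend the reason-for-leaving item to exits between birth and delivery of the placenta.

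In objective 3 and section 9.6.6, describe haemorrhage and its treatment by intended place alongside actual place, and show separately the women who left because of bleeding. State that the actual-place table is not evidence of comparative safety. Grouping by intention removes the reclassification; it does not by itself make the two groups comparable in other respects.

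The cost is one or two extra recording fields for midwives, among items already being added to E3, plus the wording. No change to care is involved.
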